Screening: COVID screening will occur prior to engaging in study activities that are being undertaken at a table in which both the study team and participants are seated in proximity to each other. COVID-19 screening will occur > 6 feet from where participants will be seated for screening and recruitment. Screening will involve the implementation of a COVID-19 screening questionnaire that is based on the content used in Johns Hopkins outpatient clinic settings. Screening will also include the assessment for fever using a temporal thermometer,

Date: 01/10/2024

Principal Investigator: [name]

Application Number: IRB00224186

which will be cleaned between individual usage. If a participant screens positive for any COVID-19 related concerns and/or is febrile, they will not be allowed to proceed with the study. Those screening positive for COVID-19 will be provided 2 recommendations: 1) COVID-19 testing at one of the Baltimore City-recommended locations (a link for Baltimore City testing locations will be provided: <https://coronavirus.baltimorecity.gov/where-get-tested-covid-19-baltimore-city>) 2 seeking or discussing medical care from their primary care physician, urgent care center, or emergency room. Participants will also be provided the date(s) for further study time points that correspond to the missed event. If they continue to demonstrate COVID-19 concerns, the same advice for testing and medical attention will be recommended. If no further study dates are available for inclusion into the study, participants will be provided the contact information to the Johns Hopkins Bayview Medical Center's Tobacco Cessation Clinic and Maryland Quitline.

Personal Protective Equipment: Study staff will wear a mask and face shield during the engagement of study activities with participants.

Screening will occur in-person over a minimum of 2 possible dates within a 1-week time interval. . The selected screening criteria was purposely kept broad to maximize generalizability and include the following:

3. ≥ 18 years of age
4. Self-reported smoker with either daily or weekly cigarette use, as well as expressed desire to reduce or quit smoking
5. Proof of residence at Douglass or Brooklyn Homes - as confirmed by verbal acknowledgement by the service coordinators at each site.
6. Working mobile phone with texting ability for the duration of the study
7. Active health insurance (for pharmacotherapy billing) – See “Notes 3 and 4 below”

Exclusion criteria:

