8. Pregnant – women will verbally acknowledge that they are *not* pregnant or trying to become pregnant in the next 8 weeks from the time of screening and recruitment to ensure no intake of nicotine and non-nicotine pharmacotherapy
9. Breastfeeding – women who are verbally acknowledge they are breastfeeding will be excluded from the study. This exclusion factor is in place secondary to breastfeeding concerns associated with the study’s usage of nicotine and non-nicotine pharmacotherapy
10. Ongoing participation in a tobacco cessation program or related tobacco intervention study. Past participation in previous iterations of the protocol is not an exclusion criteria.
11. No active health insurance.
12. Unable to verbally state that they are willing to reduce or quit smoking upon recruitment and screening
13. Adults lacking capacity to consent
14. Non-English speakers
15. Self-reported usage of *only* non-combustible tobacco products, such as smokeless tobacco or Electronic Nicotine Delivery Devices (ENDS).

Date: 01/10/2024

Principal Investigator: [name]

Application Number: IRB00224186

16. Anticipated relocation outside of Douglass or Brooklyn Homes prior to the final study visit
17. Clinical condition(s) that serve as absolute contraindications for the usage of NRT and non-NRT products and non-NRT products (Chantix®) (Reference: PMID 36280333)
 - a. Absolute contraindications of NRT products:
 - *NRT gum: Dysphagia and subsequent aspiration risk*
 - *NRT lozenge: Dysphagia and subsequent aspiration risk*
 - *NRT transdermal patch: Severe diffuse skin disease*
 - *Women who are pregnant or breastfeeding.*
 - b. Absolute contraindication of Chantix®:
 - *Inability to swallow pills*
 - *History of serious hypersensitivity or skin reactions to Chantix®*
 - *Women who are pregnant or breastfeeding*

***NOTE 1:** We will cease enrollment at 60 participants. Our aim is to enroll 30 participants at Douglass Homes and 30 participants at Brooklyn Homes. We anticipate that ≈20% of screened participants (12 people) will not continue participation at the start of the intervention. This allows enrollment and follow-up of 48 participants.

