Along with the package of medications, a stamped return envelope (addressed to PI: [name]) will be provided to allow for participants to return unused medications. Medications received by the PI will be dropped off at a drug disposal unit at Johns Hopkins Monument Street Pharmacy.

If the medications cannot be delivered by the study team on the day of pick-up from the Monument Street Pharmacy, the packaged medications will be stored in a locked cabinet in the locked office of [name] (PI). The office is located in the Division of Pulmonary and Critical Care Medicine within the Asthma and Allergy Building ([name]). Temperatures will be recorded in the office at least on a weekly basis to confirm the environment is appropriate for drug-storage.

PART 2 – START OF THE INTERVENTION (BASELINE)

Date: 01/10/2024

Principal Investigator: [name]

Application Number: IRB00224186

There are 4 steps that will occur in the start of the intervention:

1ST STEP – CONFIRMATION AND SURVEY SCREENING

This step includes the following:

- Confirmation that the participant underwent pre-screening in Time Point 1
 - We will confirm that the participant was pre-screened and consented. This confirmation will occur by asking the participant to verbally state their name, date-of-birth and place of residence. This information will be captured during the screening and stored in CRMS.
- Continued self-report of daily cigarette usage
 - If the participant reports that they are no longer smoking cigarettes, they will be provided the contact information of local smoking cessation resources in case they again start to smoke ([name] or Tobacco Treatment Clinic at Bayview Medical Center). The medications will be dropped off at a drug disposal unit at Johns Hopkins Monument Street Pharmacy.
- Baseline survey completion that contains questions about sociodemographic and smoking characteristics (see “Supplementary Document 3”).

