- **BLINDING, INCLUDING JUSTIFICATION FOR BLINDING OR NOT BLINDING THE TRIAL, IF APPLICABLE.**

This is a pre-post study design with no active comparator. All participants will receive the intervention. There is no blinding during the trial.

- **JUSTIFICATION OF WHY PARTICIPANTS WILL NOT RECEIVE ROUTINE CARE OR WILL HAVE CURRENT THERAPY STOPPED.**

Not applicable

- **JUSTIFICATION FOR INCLUSION OF A PLACEBO OR NON-TREATMENT GROUP.**

Not applicable

- **DEFINITION OF TREATMENT FAILURE OR PARTICIPANT REMOVAL CRITERIA.**

Participants will be removed if any of the following criteria are met:

- a) Smoking cessation reported at the start of the intervention (BASELINE VISIT)
 - b) Based on reported adverse medication effects, our medical specialists may recommend for discontinuation or modification of the pharmacotherapy regimen.

Date: 01/10/2024

Principal Investigator: [name]

Application Number: IRB00224186

Participants who are recommended to discontinue *BOTH* the “acute” and “controller” pharmacotherapy will be disenrolled from the study.

- **DESCRIPTION OF WHAT HAPPENS TO PARTICIPANTS RECEIVING THERAPY WHEN STUDY ENDS OR IF A PARTICIPANT’S PARTICIPATION IN THE STUDY ENDS PREMATURELY.**

If the participant’s participation ends prematurely, they will receive their reimbursement from their final study visit. They will also be provided the contact information of local smoking cessation resources, include the state quitline ([name]) and Tobacco Treatment Clinic at Bayview Medical Center.

For participants who complete the study, they too will be provided the contact information of local smoking cessation resources, include the state quitline ([name]) and Tobacco Treatment Clinic at Bayview Medical Center.

Subjects may withdraw from the study at any time without impact to their care.

5. **INCLUSION/EXCLUSION CRITERIA**

Inclusion criteria:

1. ≥ 18 years of age
2. Self-reported smoker with either daily or weekly cigarette use, as well as expressed desire to reduce or quit smoking
3. Proof of residence at Douglass or Brooklyn Homes - as confirmed by verbal acknowledgement by the service coordinators at each site.
4. Working mobile phone with texting ability for the duration of the study
5. Active health insurance (for pharmacotherapy billing)

Exclusion criteria:

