7. STUDY STATISTICS

a. Primary outcome variable

The primary endpoint will be study feasibility. Feasibility will be measured using open-ended questions administered by the research team and targeting the study stakeholders (study participants, community stakeholders and research team). The answers will serve as a means to evaluate the need for further modification in the recruitment, screening, consent, study implementation and evaluation phases of future study testing..

b. Exploratory outcome variables

Pre- & post-changes in nicotine dependence levels – Results will be stratified by baseline smoking behaviors, sociodemographic characteristics and socioeconomic stressors. For group-wise comparisons, t-test or analysis of variance will be used. Regression analyses will be performed to investigate the relationship between baseline measures and changes in smoking characteristics as the pilot study progressed.

c. Statistical plan including sample size justification and interim data analysis

Date: 01/10/2024

Principal Investigator: [name]

Application Number: IRB00224186

This study will not be powered for significance. The primary purpose of this study is to assess feasibility of the pilot study design.

d. Early stopping rules

Not applicable

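### Does the baseline check on daily smoking shut out the weekly smokers whom the inclusion criteria admit?

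*Combined protocol and SAP*

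**What the plan says.** Smoking frequency at entry is defined twice in the same words, in the screening list of Section 4 (Time Point 1) and in Section 5: "Self-reported smoker with either daily or weekly cigarette use, as well as expressed desire to reduce or quit smoking".

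At the start of the intervention (Section 4, Time Point 3, Part 2, 1st step), the list of what the step includes has the item "Continued self-report of daily cigarette usage". One instruction sits beneath it: "If the participant reports that they are no longer smoking cigarettes, they will be provided the contact information of local smoking cessation resources". Their medications then go to the pharmacy disposal unit.

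The removal criteria near the end of Section 4 have two entries. The only one based on smoking status is "Smoking cessation reported at the start of the intervention (BASELINE VISIT". The other concerns stopping both medications because of adverse effects.

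On numbers, the enrolment note (Note 1 after the exclusion criteria in Time Point 1) says "We will cease enrollment at 60 participants". It expects about 20% of those screened (12 people) to be lost, in that they "will not continue participation at the start of the intervention", which leaves 48. Section 7 makes feasibility, assessed by open-ended questions, the primary endpoint. Change in nicotine dependence is exploratory: "Results will be stratified by baseline smoking behaviors, sociodemographic characteristics and socioeconomic stressors". The study is not powered.

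**The concern.** Calling daily use continued presupposes that every participant smoked daily at screening. The inclusion criteria never required that. A weekly smoker who was correctly enrolled cannot truthfully confirm the item. Nor can a daily smoker who cut down between screening and baseline, which is quite possible in people recruited because they want to reduce or quit. For both, the protocol writes no instruction at this step.

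If staff used the item to decide who may start, eligible people could be turned away when they come for their medication. The number who start, and the reasons others do not, would then be harder to interpret in a pilot meant to study recruitment and implementation. The exploratory pre-post analysis could also lose lighter smokers.

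**Working it through.** **Planned number.** The inputs are the cap of 60 and the anticipated loss of about 20%, both from the enrolment note.

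- Expected not to continue: 60 × 0.20 = 12.
- Followed: 60 - 12 = 48, which matches the stated figure.

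**Who is affected by each rule.** The statements can be applied to every kind of participant who might arrive at baseline.

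| Smoking at screening | Smoking at baseline | Eligible at screening | Fits the word daily at baseline | Meets the action under the item (no longer smoking) | Meets the cessation removal criterion |
|---|---|---|---|---|---|
| Daily | Daily | Yes | Yes | No | No |
| Weekly | Weekly | Yes | No | No | No |
| Daily | Weekly | Yes | No | No | No |
| Daily or weekly | Less than weekly | Yes | No | No | No |
| Daily or weekly | None | Yes | No | Yes | Yes |

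The last two columns agree in every row. The instruction under the item opens with "If the participant reports that they are no longer smoking cigarettes", and the removal criterion names the same event. The mismatch is confined to the middle column, in rows two to four, and no consequence is attached to that column.

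**Effect on the numbers.** Continuing smokers removed under the written rules: 0. Planned follow-up: 48 - 0 = 48.

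**Is the item an entry test?** It stands in a list of visit activities that also includes completing the baseline survey. No sentence says that a participant must smoke daily to proceed. The phrase might also refer to the amount smoked per day, since the patch dosing table in Section 6 asks about cigarettes per day. The word continued makes that reading less natural, so nothing here relies on it.

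**Effect on the analyses.** The primary endpoint does not use smoking frequency. Section 7 stratifies the exploratory results by baseline smoking behaviors but does not define a daily versus non-daily stratum. No power calculation exists that could be disturbed.

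**Could a size be given for a misreading?** No. The documents state no expected share of non-daily smokers, and the 48 is only what the anticipated loss allows. No decision or precision target depends on it.

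**The case for a change.** The best argument for an edit is practical. Staff at the visit work from the step in front of them, and that step says daily. Its title describes it as confirmation and screening, so use as a gate is a plausible misreading. The rule that keeps a weekly smoker in has to be inferred from a sub-item and from a list several pages later. The screening criteria were deliberately kept broad for generalizability, and a daily-only reading would work against that. Changing one phrase costs no participants, visits or procedures.

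Part of this stands. The mismatch is real, it lies in the current text, and it is not an artefact of how the text was extracted. Anyone revising the document for another reason could reasonably align the places, with the study team stating the rule it intends.

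The harm does not stand. It requires staff to apply a test that the protocol never states, and to remove someone on grounds missing from the removal criteria. The absence of a separate instruction for a continuing non-daily smoker is not a gap in itself: a participant who meets no removal rule goes on to the next step. A request to record baseline smoking frequency would also be unsupported. The baseline survey already collects smoking characteristics, and its content (Supplementary Document 3) is not among the documents available here.

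**Conclusion.** This is a clerical slip, and the plan need not change. One word in the baseline step is narrower than the inclusion criteria, while both statements that carry a consequence refer only to reported cessation. As written, no continuing smoker is removed because of the item, the planned 48 is unaffected, and the primary endpoint and exploratory analysis stay as they are.

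The conclusion assumes that staff follow the written action and the removal criteria rather than treat the item as a requirement of its own. It also assumes that the baseline form, which cannot be seen here, does not turn the item into an entry condition. If it did, the conflict would have practical effect and the passages would have to be reconciled. Nothing in the documents points that way.
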